1. SCIENTIFIC BACKGROUND

Congenital morphological features are evaluated not only as anatomical variations but also as structural characteristics associated with neuromuscular organization and physical performance. Considering that athletic performance is shaped by the individual's structural characteristics alongside training load and technical skills, the examination of the potential significance of certain morphological phenotypes for performance appears meaningful. In this context, one of the notable morphological variations is Morton toe, a congenital foot morphology characterized by a longer second toe relative to the first (Decherchi, 2005).

From an etiological perspective, it has been proposed that this morphological variation may serve as an indirect marker of prenatal androgen exposure during fetal development (Harrison, 2010; Hönekopp & Watson, 2010; Saino et al., 2006). In addition, experimental animal models have reported an increasing tendency in type II muscle fiber proportion under conditions of prenatal hyperandrogenization (Abbott et al., 2012; Huber et al., 2017; DeChick et al., 2020). These muscle fibers are associated with neuromuscular performance components requiring high speed and power. When these findings are considered collectively, it can be theoretically proposed that individuals with the Morton toe phenotype may exhibit differentiated neuromuscular characteristics. However, the direct and experimental evaluation of this relationship in humans appears challenging due to ethical and methodological constraints. Therefore, indirect approaches through morphological phenotypes offer a meaningful research framework for examining the possible reflections of these biological mechanisms on human performance.

In the existing literature, Morton toe has predominantly been addressed as a clinical and orthopedic variation, associated with metatarsal stress fractures, balance performance, and musculoskeletal problems (Chuckpaiwong et al., 2007; Davidson et al., 2007; Agopyan et al., 2011; Kim, 2024). In contrast, a limited number of studies conducted in athletic populations suggest that second toe length may be associated with certain performance indicators (Kulthanan et al., 2004; Tanaka et al., 2017; Tomita et al., 2018). However, these studies have largely focused on isolated morphological measurements, and the relationship between Morton toe and neuromuscular properties and performance outcomes has not been addressed in the literature with an integrative approach.

In light of previous reports, whether Morton toe constitutes an anatomical variation that creates a disadvantage for athletic performance or a phenotype associated with neuromuscular performance is not clear in the literature. In this context, the present study aimed to examine the potential differences in neuromuscular properties and kinetic performance parameters between female football players with Morton toe and those with normal foot morphology.

2. STUDY OBJECTIVES AND HYPOTHESES

2.1. Primary Objective

To compare neuromuscular contractile properties (tensiomyographic contraction time, Tc) and kinetic performance (reactive strength index, RSI) between female football players with Morton toe morphology and those with normal foot morphology.

2.2. Secondary Objective

To compare additional tensiomyographic parameters (Tr, Td, Ts, Dm) and kinetic performance variables (jump height, peak power/BM, landing net peak force/BM) between groups.

2.3. Hypotheses

Primary hypothesis: Female football players with Morton toe morphology would exhibit faster neuromuscular contractile properties and higher reactive strength compared to those with normal foot morphology.

Secondary hypothesis: Morton toe morphology would be associated with higher jump height and peak power values compared to normal foot morphology.

3. STUDY DESIGN

This study was designed as a cross-sectional, observational, group comparison investigation. Following assessment of foot morphology, participants meeting the inclusion criteria were classified into two groups: Morton foot group (MG) and normal foot group (NG). All participants underwent neuromuscular and kinetic measurements in a single testing session.

As all participants were active football players, measurements were conducted during the off-season (transition period) within the annual training periodization to minimize confounding effects of intensive training loads. To reduce potential variability related to circadian rhythm, all measurements were performed within the same time-of-day window (± 1 hour) for each participant. Participants were instructed to avoid intense physical activity for 24 hours, heavy meals for 3 hours, caffeine for 12 hours, and alcohol for 24 hours prior to testing.

The standardized testing sequence for all participants was: foot morphology assessment, tensiomyography (TMG) measurement, standard warm-up protocol, followed by drop jump test. Standard rest intervals were provided between test stages to prevent acute fatigue from affecting measurement results. All tests were performed in the same laboratory environment, by the same researcher, using the same equipment and standardized procedures.

To minimize measurement and analysis bias, blinding procedures were implemented. Participants were not informed about the specific research topic, and group information was not disclosed. The researcher performing TMG and drop jump measurements was blinded to participants' group classification (single-blind). Statistical analysis was performed by an independent researcher using a coded dataset.

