4. PARTICIPANTS

4.1. Study Population

A total of 47 female football players (age: 20.72 ± 2.76 years) who held a valid sports license for the relevant season and were actively participating in competitive matches volunteered to participate. Prior to the study, participants were provided with detailed information regarding the research protocol and written informed consent was obtained.

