4.4. Group Classification

Participants were classified into two groups based on bilateral foot morphology assessed using the palpation-based metatarsal length measurement technique described by Davidson et al. (2007) and validated by Martínez-Cepa et al. (2014). Based on the reported minimal detectable change (MDC = 0.30 mm), participants with bilateral metatarsal differences ≤ -0.30 mm were classified as Morton foot group ($n = 24$), while those with bilateral differences $> +0.30$ mm were classified as normal foot group ($n = 23$). Values between -0.30 and $+0.30$ mm were classified as indeterminate and excluded.

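### Section 3 gives every test, including the foot measurement that defines group, to one researcher, yet calls the TMG and drop jump operator blinded: assessor blinding is unsupported as written

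*Protocol*

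**What the plan says.** Three statements in section 3 of the protocol bear on this point.

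- The order of testing: "The standardized testing sequence for all participants was: foot morphology assessment, tensiomyography (TMG) measurement, standard warm-up protocol, followed by drop jump test".
- The operator: "All tests were performed in the same laboratory environment, by the same researcher, using the same equipment and standardized procedures".
- Blinding of the outcome assessor: "The researcher performing TMG and drop jump measurements was blinded to" group, with the label single-blind. This is offered as a safeguard against bias in measurement and analysis. A further sentence says that an independent analyst worked on coded data.

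Section 4.4 ties group to the foot measurement and nothing else: "participants with bilateral metatarsal differences ≤ -0.30 mm were classified as Morton foot group". The normal group is those with differences above +0.30 mm on both feet, and values in between are excluded. Section 5.4 describes how the distances for the first and second metatarsals are obtained by palpation and caliper and subtracted. Section 5.8 names Tc (from TMG) and RSI (from the drop jump) as the primary outcomes.

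**The concern.** Assessor blinding is the only protection the protocol claims at the point where Tc and RSI are measured. If the person who ran TMG and the jumps had already measured the feet, that protection did not exist.

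Both outcomes leave room for the operator. For TMG (section 5.5), the operator finds the muscle by palpation, places the probe and electrodes, and raises the current until displacement is maximal; Tc is then read from that displacement curve. For RSI (section 5.6), the operator conducts the practice jumps and three maximal efforts. The primary hypothesis in section 2.3 is directional, so an operator aware of group would also know which result was expected.

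Coding the dataset for the analyst protects the analysis stage only. The regression models in section 6 adjust for age, body mass index and arch index. They cannot remove an operator effect that runs along the group line.

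**Working it through.** No sample size, power or alpha figure enters this point, so there is nothing to compute. The check sets the statements side by side.

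1. **What defines group?** The metatarsal difference on both feet, by fixed cut-offs: ≤ -0.30 mm is Morton, > +0.30 mm is normal (sections 4.2, 4.4 and 5.4). No other information enters.
2. **What does the person measuring the feet learn?** Two distances per foot, whose difference is the classifying variable (section 5.4). That section is in the passive voice and does not say who did the subtraction, but whoever held the calipers had both numbers.
3. **When is this learned?** Before the outcome tests. Section 3 lists the foot assessment as the first stage, ahead of TMG and the drop jump.
4. **Who did it?** Section 3 follows that list directly with a statement that one researcher performed all tests. The foot assessment is one of the listed stages, so on a plain reading it is included.
5. **What is claimed?** That the TMG and drop jump operator did not know group.

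From 1 to 4, the operator had the classifying measurement before starting TMG, which contradicts 5. At least one of three statements must give way: the sequence as a list of tests, the single researcher, or the blinding.

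6. **Does anything elsewhere resolve it?** No section names a separate foot assessor. No section says that the foot result, or the feet themselves, were concealed from the outcome operator.
7. **Does the contradiction need the foot assessment to be in the same session?** No. The sentence "All participants underwent neuromuscular and kinetic measurements in a single testing session" does not mention foot morphology. The conflict rests on the same person doing both, whether on one day or two.

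**The case against.** The best case on the other side is that the one-researcher sentence is about standardisation. It sits beside the same laboratory and the same equipment, and may mean that each test had one constant operator across participants. The next paragraph singles out the researcher who ran TMG and the jumps, which would be an odd description if one person did everything. Foot morphology also decided eligibility: section 4.6 starts from 97 players and removes 10, 14 and 26 to reach 47, the 26 for feet that did not agree. That fits a separate screening step, perhaps by another person.

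This reading is possible, and it stands as a reason not to treat unblinding as established. It does not rescue the text, which says none of it and would still need its operator statement corrected.

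A reader might also draw stronger conclusions that the documents do not support:

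- **That the operator did know group, and that Tc and RSI were pushed towards the hypothesis.** The documents show an unsupported claim of blinding, not an event. Parts of the procedure are fixed by rule: current rises in 10 mA steps, Tc has a set definition, and the jump with the highest RSI of three is taken. Discretion remains in placement and in how maximal efforts are conducted.
- **That participant blinding is contradicted too.** Section 3 says "Participants were not informed about the specific research topic, and group information was not disclosed", while section 4.1 says "participants were provided with detailed information regarding the research protocol". These are compatible: procedures can be explained in detail without revealing the Morton toe hypothesis or a person's group.
- **That the false positive rate is inflated by a known amount.** Any such figure would come from an assumed operator shift, for which the documents give no basis.

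**Conclusion.** The point holds as an internal contradiction in section 3. As written, assessor blinding is not supported for either primary outcome, and this applies to all 47 participants (24 Morton, 23 normal). Because Tc and RSI have operator-dependent steps, knowledge of group could bias both. The size of any such bias cannot be stated from the documents.

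The conclusion assumes the plain reading, under which the foot assessment is one of the tests done by the single researcher. If each test had its own constant operator and the foot result was concealed, the blinding claim may be true and the operator sentence is what is wrong. Either way section 3 must be corrected. Who measured what, and who was blinded, belongs in the protocol, and this protocol states it inconsistently. Correction is required because a reader would otherwise credit both primary comparisons with a safeguard that the described procedure rules out.

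**What to change.** Establish who measured the feet and reconcile section 3 accordingly.

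- **If one researcher did both the foot assessment and the outcome tests:** delete the assessor-blinding statement and the single-blind label. Keep only the claim that the analyst worked on coded data. Report unblinded outcome assessment as a limitation when interpreting Tc and RSI. Possible wording: *The researcher who measured Tc and RSI had also measured foot morphology and was not blinded to group; only the statistical analyst was.*
- **If a different person assessed the feet:** correct the one-researcher sentence so that it refers to a constant operator within each test. State by role who measured morphology, and how the result was concealed from the TMG and drop jump operator until testing was finished. The blinding claim can then stay.

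The cost is a few sentences in section 3, plus a limitation statement in the report in the first case. No new data and no reanalysis are needed. Re-reading stored recordings under coded identifiers should not be made a condition: it could not undo probe placement or the conduct of the jumps, and the protocol does not say that raw files were kept.

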4. PARTICIPANTS

4.1. Study Population

A total of 47 female football players (age: 20.72 ± 2.76 years) who held a valid sports license for the relevant season and were actively participating in competitive matches volunteered to participate. Prior to the study, participants were provided with detailed information regarding the research protocol and written informed consent was obtained.

4.2. Inclusion Criteria

(a) Active female football players with a valid sports license; (b) regular participation in training and competitive matches; (c) bilateral Morton toe morphology ($\Delta \leq -0.30$ mm on both feet) or bilateral normal foot morphology ($\Delta > +0.30$ mm on both feet); (d) body mass index between 18.5 and 29.9 kg/m²; (e) bilateral arch index between 14% and 29%.

4.3. Exclusion Criteria

(a) Serious lower-extremity musculoskeletal injury within the past 12 months; (b) neurological or orthopedic disease affecting measurement procedures; (c) current pharmacological use affecting performance; (d) acute pain, injury, or illness on measurement day; (e) menstruation on measurement day (self-reported); (f) inconsistent bilateral foot morphology classification between feet.

4.4. Group Classification

Participants were classified into two groups based on bilateral foot morphology assessed using the palpation-based metatarsal length measurement technique described by Davidson et al. (2007) and validated by Martínez-Cepa et al. (2014). Based on the reported minimal detectable change (MDC = 0.30 mm), participants with bilateral metatarsal differences ≤ -0.30 mm were classified as Morton foot group ($n = 24$), while those with bilateral differences $> +0.30$ mm were classified as normal foot group ($n = 23$). Values between -0.30 and $+0.30$ mm were classified as indeterminate and excluded.

4.5. Sample Size Calculation

Sample size was calculated based on the effect size reported by Tanaka et al. (2017), who examined the relationship between forefoot bone lengths and performance in male sprinters. The effect size for second metatarsal bone length differences between fast and slow sprinters (Cohen's $d = 1.04$) was used as a reference. With a significance level of $\alpha = 0.05$, statistical power of 0.95, and effect size of 1.04, a minimum of 21 participants per group was required. The final sample of 24 and 23 participants per group exceeded this requirement.

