5.8. Outcome Variables

Primary outcomes were determined a priori as contraction time (Tc) and reactive strength index (RSI). Secondary outcomes included relaxation time (Tr), delay time (Td), sustain time (Ts), maximal displacement (Dm), jump height (JH), peak power normalized to body mass (PPI), and landing net peak force normalized to body mass (LPF).

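### The 0.95 power in section 4.5 rests on a bone-length effect in male sprinters, so it is not a power for Tc or RSI, and its 21 per group needs an unstated one-sided test

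*Protocol*

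**What the plan says.** Protocol section 4.5 takes its effect size from a research group "who examined the relationship between forefoot bone lengths and performance in male sprinters". The quantity is given as "The effect size for second metatarsal bone length differences between fast and slow sprinters", with Cohen's d = 1.04, and the text describes it as a reference value. At a significance level of 0.05, "statistical power of 0.95, and effect size of 1.04", the section concludes that "a minimum of 21 participants per group was required". It then adds: "The final sample of 24 and 23 participants per group exceeded this requirement".

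Sections 2.1 and 5.8 name two primary outcomes: Tc, measured by tensiomyography on the vastus lateralis, and RSI, from a drop jump. Both are compared between Morton and normal foot groups of female football players.

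The primary hypothesis in section 2.3 is directional: the Morton group "would exhibit faster neuromuscular contractile properties and higher reactive strength compared to those with normal foot morphology". Section 6 names the independent samples t-test, or the Mann-Whitney U test if normality fails, at 0.05 with no correction for Tc and RSI. Neither section 4.5 nor section 6 says whether the tests are one-sided or two-sided.

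**The concern.** A power figure belongs to a particular comparison: a given outcome, with its own standard deviation, between groups formed in a given way. The d of 1.04 describes a bone length in male sprinters split by speed. The study measures a muscle contraction time and a jump index in female football players split by foot type. Outcome, grouping, sex and sport all differ. Section 4.5 gives no expected difference, standard deviation or smallest important effect for Tc or RSI, and no reason why 1.04 should apply to them.

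The unstated side matters as well. If the tests are two-sided, the minimum of 21 does not follow from the section's own inputs, and the statement that the final sample exceeds the requirement is wrong.

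At stake is what the protocol tells readers about the study's sensitivity. The validity of the tests and the type I error are not affected.

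**Working it through.** **Inputs.** From section 4.5: d = 1.04, significance level 0.05, power 0.95, stated minimum 21 per group, achieved groups of 24 and 23. From section 6: independent samples t-test. Not given: the side of the test, and any effect size for Tc or RSI.

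**Step 1. Reproduce the stated 21.** The normal approximation is n per group = 2 × [(z_α + z_0.95) / d]².

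- One-sided: 2 × [(1.645 + 1.645) / 1.04]² = 20.01, rounded up to 21.
- Two-sided: 2 × [(1.960 + 1.645) / 1.04]² = 24.03, rounded up to 25.

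The exact calculation (noncentral t) gives 20.73, so 21, one-sided, and 25.03, so 26, two-sided. The stated 21 is reproduced one-sided by both methods and two-sided by neither.

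**Step 2. Power at d = 1.04.** The noncentrality is δ = d × √[n₁n₂ / (n₁ + n₂)], with n₁ + n₂ − 2 degrees of freedom.

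- 21 per group: δ = 1.04 × √(441/42) = 1.04 × 3.240 = 3.370, 40 degrees of freedom. Power is 0.952 one-sided and 0.908 two-sided.
- 24 and 23: δ = 1.04 × √(552/47) = 1.04 × 3.427 = 3.564, 45 degrees of freedom. Power is 0.969 one-sided and 0.937 two-sided.

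Two-sided, the achieved sample therefore falls short of 0.95 even if 1.04 is accepted.

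**Step 3. What 24 and 23 players can detect.** Solving the same formula for d at 0.05:

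| Power | Two-sided d | One-sided d |
|---|---|---|
| 0.80 | 0.84 | 0.74 |
| 0.95 | 1.08 | 0.97 |

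**Step 4. Power over a range of d.** The protocol gives no effect for Tc or RSI, so the values of d below 1.04 are assumptions for illustration.

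| d | Two-sided | One-sided |
|---|---|---|
| 0.3 | 0.17 | 0.26 |
| 0.5 | 0.39 | 0.52 |
| 0.6 | 0.52 | 0.65 |
| 0.8 | 0.77 | 0.85 |
| 1.04 | 0.94 | 0.97 |

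Power of 0.95 on Tc or RSI is reached only if the true standardised difference is about 1.0 or more, whichever side is used.

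**The case against.** The strongest defence is that section 4.5 hides nothing. It names the source population and the quantity, and it calls the value a reference. Every power figure is conditional on its assumed effect, and the section never presents 1.04 as an estimate for Tc or RSI. This stands in part: the fault is an unjustified proxy, not a concealed one. But disclosing a source does not justify the transfer, and the section goes on to conclude that the sample meets the requirement.

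It can also be said that an association may be viewed from either side, so the swap of grouping and measured variable does not by itself rule out the reference. That is fair. The different outcome and population carry the point.

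The directional hypothesis makes a one-sided calculation plausible, and then 21 is arithmetically correct. That also stands, which is why both sides are shown. Section 6 states no side, however, and a directional hypothesis alone does not fix one.

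Finally, the 47 players are already classified, so the sample size is settled and no estimate or p value changes. This limits the weight of the point but does not make the power statement right.

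A reader might infer that the protocol invites a non-significant result to be taken as evidence of no difference. No section says so. Section 6 already plans mean differences and Hedges' g with 95% confidence intervals for parametric comparisons. Only the nonparametric branch, where r is planned without a stated interval, lacks this.

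**Conclusion.** The point holds as a fault in the justification and wording of section 4.5. The stated 0.95 is not a power for Tc or RSI. The 21 per group follows from the section's inputs only under a one-sided test that the protocol does not state. Two-sided, 26 per group are needed at d = 1.04, and the achieved sample gives 0.937.

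The results rest on the t-test branch of section 6, a level of 0.05 for each primary outcome as the protocol sets it, and groups of 24 and 23. The detectable differences need no assumption about the true effect; the power values at smaller d do.

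Two further readings go beyond the document. One is that the study would more likely miss a moderate effect than find it. That depends on the side and on what counts as moderate: at d = 0.5 power is below one half two-sided but 0.52 one-sided, and at d = 0.6 it is 0.52 even two-sided. The other is that no earlier estimate for Tc or RSI existed. The protocol gives none, which is not the same; only the sponsor can confirm it.

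The correction is worth making because the headline power is unsupported for both primary outcomes.

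**What to change.** Reword section 4.5 in three places.

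1. State whether the calculation and the primary tests are one-sided or two-sided, and use the same side in section 6. It should be the side on which the analysis was planned, not one chosen to preserve the 21. If two-sided, change the minimum at d = 1.04 to 26 per group and remove the statement that the final sample exceeds the requirement.
2. Say that d = 1.04 is a proxy drawn from another outcome and another population.
3. Replace the 0.95 claim with a sensitivity statement, for example:

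> With 24 and 23 players and a two-sided t-test at 0.05, each primary outcome has 80% power for a standardised difference of 0.84 and 95% power for 1.08.

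If the test is one-sided, the two values become 0.74 and 0.97. The sponsor may add that no earlier Tc or RSI estimate was found, if it can confirm this.

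The cost is a few sentences. No participants are added and no analysis changes. The drawback for the sponsor is that the stated figure becomes less favourable.

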6. STATISTICAL CONSIDERATIONS

Statistical analyses were performed using SPSS software (Version 27.0, IBM Corp., Armonk, NY, USA). Continuous variables were presented as mean \pm standard deviation for normally distributed data and median [interquartile range] for non-normally distributed data. Normality was assessed using the Shapiro-Wilk test. The significance level was set at $\alpha = 0.05$.

Between-group comparisons were performed using independent samples t-test for normally distributed variables and Mann-Whitney U test for non-normally distributed variables.

Primary outcome variables (Tc and RSI) were designated a priori and were not subjected to multiple comparisons correction. For secondary outcome variables (Tr, Td, Ts, Dm, JH, PPI, LPF), the Holm-Bonferroni sequential correction was applied to control the family-wise error rate. Both uncorrected and corrected p values were reported.

Effect sizes were calculated as Hedges' g with 95% confidence intervals for parametric comparisons and $r (Z/\sqrt{N})$ for nonparametric comparisons. Mean differences with 95% confidence intervals were reported for parametric comparisons only.

Supportive multiple linear regression models were constructed separately for each primary outcome (Tc and RSI). The dependent variable was the respective performance parameter, and independent variables were group (Morton = 1, normal = 0), age, body mass index, and mean bilateral arch index (Mean AI). Left and right arch indices were combined into a single mean variable to reduce multicollinearity. Regression diagnostics included residual normality assessed by Shapiro-Wilk test and multicollinearity assessed by variance inflation factor (VIF). These analyses were used as supportive evidence for the independence of group effects from potential confounders.

Figures and data visualizations were prepared using GraphPad Prism (version 10.4.1).

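### The minimum of 21 per group holds only for a one-sided test that the protocol never declares; read as two-sided, as section 6 suggests, the requirement is 26 per group and 24/23 gives power of about 0.94

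*Protocol*

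**What the plan says.** Section 4.5 takes its effect size from a study of male sprinters: "The effect size for second metatarsal bone length differences between fast and slow sprinters (Cohen's $d = 1.04$) was used as a reference". From alpha 0.05 it then concludes: "statistical power of 0.95, and effect size of 1.04, a minimum of 21 participants per group was required". It closes with: "The final sample of 24 and 23 participants per group exceeded this requirement".

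Section 6 sets alpha at 0.05 and does not say whether it is one- or two-sided. On the tests it says: "Between-group comparisons were performed using independent samples t-test for normally distributed variables and Mann-Whitney U test for non-normally distributed variables". On reporting it says: "Mean differences with 95% confidence intervals were reported for parametric comparisons only". Hedges' g also carries a 95% interval.

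Section 2.3 states the primary hypothesis with a direction: players with Morton toe "would exhibit faster neuromuscular contractile properties and higher reactive strength compared to those with normal foot morphology". The objectives in sections 2.1 and 2.2 are neutral and speak only of comparing the groups. The background in section 1 leaves open whether Morton toe is a disadvantage for performance or a phenotype associated with it.

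**The concern.** A sample size for a comparison of two means depends on whether alpha is spent in one tail or two, and section 4.5 does not say which. Its result fits one tail only, while section 6 reads as two tails. If the analysis is two-sided, the stated minimum is too low by five per group and the sentence that the sample exceeded the requirement is wrong.

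More than the stated power is at stake. Sidedness decides whether a primary result in the hypothesised direction with a two-sided p-value between 0.05 and 0.10 counts as positive. The two primary outcomes, Tc and RSI, are tested without multiplicity correction, and recruitment is already complete. The rule should therefore be on record and not left to be inferred from the data section by section. A one-sided 0.05 test reported with an ordinary 95% interval can also be called significant while that interval includes zero.

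**Working it through.** **Inputs.** From section 4.5: d = 1.04, alpha = 0.05, power = 0.95, final groups of 24 and 23. From section 6: independent samples t-test. Allocation is taken as 1:1 for the minimum. No dropout allowance applies, because testing is in a single session.

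**Step 1: normal approximation.** n per group = 2(z_alpha + z_power)² / d², with d² = 1.0816 and z_power = 1.645.

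- One-sided: 2(1.645 + 1.645)² / 1.0816 = 20.01, rounded up to **21**.
- Two-sided: 2(1.960 + 1.645)² / 1.0816 = 24.03, rounded up to **25**.

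**Step 2: exact power of the t-test.** The statistic follows a noncentral t distribution with df = n1 + n2 − 2 and noncentrality d·√(n1·n2/(n1 + n2)). Power is the probability beyond the critical value t(1 − alpha) for a one-sided test, or beyond ±t(1 − alpha/2) for a two-sided test.

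For example, at 24/23 the noncentrality is 1.04 × √(552/47) = 3.564 with 45 df. The critical value is 1.679 one-sided and 2.014 two-sided.

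| Groups | Noncentrality | One-sided power | Two-sided power |
|---|---|---|---|
| 20/20 | 3.289 | 0.9435 | 0.8934 |
| 21/21 | 3.370 | 0.9523 | 0.9079 |
| 24/23 | 3.564 | 0.9689 | 0.9366 |
| 25/25 | 3.677 | 0.9761 | 0.9498 |
| 26/26 | 3.750 | 0.9800 | 0.9570 |

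**Step 3: compare with the protocol.** One-sided, 20 per group falls short of 0.95 and 21 reaches it, so the protocol's 21 is reproduced exactly. Two-sided, 25 per group falls just short (0.9498) and the minimum is 26. A two-sided minimum of 21 per group corresponds to power 0.90, not 0.95.

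**Step 4: size of the gap if two-sided.** At the achieved sample, 0.95 − 0.937 = 0.013, so the type II error is 6.3% against a planned 5%. At the stated minimum of 21 per group it would be 9.2%, but that sample was not the one obtained. The effect detectable with power 0.95 at 24/23 moves from 1.04 to about 1.075.

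**Step 5: does the rank test explain the 21?** With normal data the Mann-Whitney U test has asymptotic relative efficiency of about 0.955. Scaling the sample size by this gives 22 one-sided and 27 two-sided, so it does not account for 21.

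**The case against.** The strongest reply is that 21 is not an arithmetic error. It is the correct one-sided answer, and section 2.3 supplies a direction for both hypotheses. The protocol nowhere says two-sided. The 95% intervals may be descriptive reporting and not the decision rule, and naming a t-test does not fix the number of tails. Sidedness might also be settled in an analysis plan that is not shown. If the tests are one-sided, 24 and 23 do exceed the requirement, with power 0.969.

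Much of this stands. A reader might infer that the sample size is simply miscalculated, or that the study is materially underpowered, and the protocol supports neither reading. The two-sided reading of section 6 is a strong inference, not a statement in the text. Even on that reading the shortfall at the achieved sample is 1.3 points.

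It is also fair to say that the choice of d matters more. The value describes bone length in male sprinters, not Tc or RSI in female footballers. If the true d were 0.8 (an assumption for illustration), two-sided power at 24/23 would be 0.765; at 0.5 it would be 0.389.

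What the reply does not remove is the mismatch. A directional hypothesis is an expectation about the result; it does not specify a one-sided test. The neutral objectives, and a background that leaves a disadvantage open, make an undeclared one-sided test harder to assume. Section 4.5 also goes beyond leaving a detail for later: it gives a specific number and a specific conclusion, and these disagree with the analysis as section 6 reads.

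**Conclusion.** The point holds as an unreconciled inconsistency, of minor to moderate severity. The stated minimum implies one-sided alpha 0.05; the analysis section reads as two-sided alpha 0.05; the protocol states neither.

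- If two-sided: the minimum is 26 per group, the achieved 24 and 23 fall short of it, and power is 0.937, not 0.95.
- If one-sided: 21 is right, the final sample exceeds it, and power is 0.969.

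These figures assume d = 1.04, normal data with equal variances, and the t-test. They say nothing on whether d = 1.04 is a realistic effect for Tc or RSI.

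**What to change.** State the sidedness of the primary tests in both section 4.5 and section 6, and make the two agree.

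- **If two-sided, as section 6 reads:** replace 21 with 26 per group, state that 24 and 23 give power of about 0.94 for d = 1.04, and delete the sentence that the final sample exceeded the requirement.
- **If one-sided testing was truly planned before the data were seen:** say so, justify it against the open question in section 1, and align the reported intervals with it (a one-sided 95% bound or a two-sided 90% interval). The 21 then stands, and power at 24/23 is 0.969.

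In both cases, present the power as conditional on the borrowed effect size, so that the restated figure does not give false reassurance.

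The cost is a few sentences in the protocol and the report. On the two-sided route the stated figure becomes slightly less favourable. No further enrolment is needed.
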